### 6.2.7 Prohibited Concomitant Medications

The following medications are excluded while the patient is receiving entinostat:

- Any other HDAC inhibitor, including valproic acid
- DNA methyltransferase inhibitors
- Any additional anticancer agents, such as chemotherapy, immunotherapy, targeted therapy, biological response modifiers, or endocrine therapy, will not be allowed, even if utilized as treatment of non-cancer indications.
- Any investigational agents
- Radiation therapy

*Note: Radiation therapy to a symptomatic solitary lesion or to the brain may be considered on an exceptional case-by-case basis after consultation with Sponsor. The patient must have clear measurable disease outside the radiated field. Administration of palliative radiation therapy will be considered clinical progression.*

- Traditional herbal medicines; these therapies are not fully studied and their use may result in unanticipated drug-drug interactions that may cause or confound the assessment of toxicity

Medications to be Avoided During the Study:

- Sensitive substrates of CYP1A2, CYP2C8, CYP3A with a narrow therapeutic window (see Appendix)
- Drugs that are known to inhibit or induce P-gp (see Appendix B)

## 6.3 ***Hydroxychloroquine***

6.3.1 Generic name: Hydroxychloroquine sulfate

6.3.2 Commercial name: Plaquenil

6.3.2 Availability: Hydroxychloroquine is commercially available and patients will be given prescriptions to be filled at their local pharmacy

6.3.4 Route of administration: Oral

6.3.5 Nursing/Patient Instructions: Hydroxychloroquine should be taken by swallowing the whole tablet in rapid succession without chewing. Patients receiving antacids, sucralfate, cholestyramine, and/or bicarbonate should have the HCQ drug dose administered at least 1 hour before or 2 hours after these medications.

6.3.6 **Table 10: Potential Toxicities of Hydroxychloroquine**

Central Nervous System	Irritability, nervousness, emotional changes, nightmares, psychosis, headache, dizziness, vertigo, seizure, ataxia, lassitude
Dermatologic	Bleaching of hair, alopecia, pigmentation changes (skin and mucosal; black-blue color), rash (urticarial, morbilliform, lichenoid, maculopapular, purpuric, erythema annulare centrifugum, Stevens-Johnson syndrome, acute generalized exanthematous pustulosis, and exfoliative dermatitis)
Gastrointestinal	Anorexia, nausea, vomiting, diarrhea, abdominal cramping
Hematologic	Aplastic anemia, agranulocytosis, leukopenia, thrombocytopenia, hemolysis (in patients with glucose-6-phosphate deficiency)
Hepatic	Abnormal liver function/hepatic failure (isolated cases)
Neuromuscular & Skeletal	Myopathy leading to progressive weakness and atrophy of proximal muscle groups (may be associated with mild sensory changes, loss of deep tendon reflexes, and abnormal nerve conduction)
Ocular	Disturbance in accommodation, keratopathy, corneal changes/deposits (visual disturbances, blurred vision, photophobia - reversible on discontinuation), macular edema, atrophy, abnormal pigmentation, retinopathy (early changes reversible - may progress despite discontinuation if advanced), optic disc pallor/atrophy, attenuation of retinal arterioles, pigmentary retinopathy, scotoma, decreased visual acuity, nystagmus

\*\*For complete information about hydroxychloroquine, please see the FDA package insert

## 7.0 STATISTICS

### 7.1 Primary Endpoints

#### 7.1.1 Phase I

The Phase I methodology will be a standard Phase I escalating trial with three patients per level, expanding to six patients per level in the event of dose-limiting toxicity at any level, and provision for expansion to 20 additional patients at the recommended Phase II dose to better characterize the optimal dose and the variation in toxicity at that level. A minimum of 4 weeks of combination therapy with hydroxychloroquine, entinostat, and regorafenib are required in the third patient before escalation to the next dose is initiated. At the MTD, at least 6 patients must be treated for 2 cycles to evaluate chronic toxicity and determine the RP2D (see section 4.3 for details).

We will calculate the percentage of subjects with toxicities at each dose level. We expect that doses close to full single agent doses will be tolerable. Three patients will be initially treated at each dose level. The plan for escalation is described below:

Three patients will initially be treated at each dose level.

If 0/3 patients experience DLT, then the dose will be escalated.

If 2-3/3 patients experience DLT, then the MTD has been exceeded. Three additional patients are treated at the previous dose (if only 3 had been treated) as a total of 6 patients must be treated at the MTD.

If 1/3 patients experience DLT, then 3 additional patients are treated. If none of the additional patients develop DLT, then the dose will be escalated, otherwise escalation ceases and the previous dose will be expanded to a total of 6 patients.

To assure safety in this phase I study, the operating characteristics of the escalation rule to be employed have been determined. The operating characteristics denote the probability of escalation to the next dose level, for a given true DLT rate. For a true DLT that is high, we desire the probability of escalation to be low. As noted in the table, the probability of escalating beyond a certain dose level, if that dose level truly has a 10% DLT rate, is 0.91. On the other hand, if the true DLT rate is 40%, there is only a 31% chance of dose escalation.

**Table 11: Operating Characteristics of the Escalation Rule**

True DLT Rate	Probability of Escalation
.1	.91
.2	.71
.3	.49
.4	.31
.5	.17
.6	.08
.7	.03
.8	.01

### 7.1.2 Phase II

Single agent regorafenib showed ORR of 1% in phase III trials in advanced colorectal cancers. We anticipate being able to improve this response rate substantially, perhaps to 15% or more. We will enroll a total 26 patients at the RP2D, including those treated during the phase I portion of the study. Sample size calculations are based on an assumption of at least 20 evaluable patients. With 20 patients, an exact binomial test with a 0.05 one-sided significance level will have 84% power to detect an improvement from the historical rate (null hypothesis proportion) of 1% to an improved rate (alternative proportion) of 15%.

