### ***2.5 Regorafenib Clinical Experience***

Regorafenib is a multikinase inhibitor with effects on angiogenesis via the VEGF pathway as well as various cell growth pathways. It is closely related to sorafenib, differing in structure by a single fluorine molecule. The principle tyrosine kinase targets of regorafenib include VEGFR1-3, PDGR- $\beta$ , KIT, RAF-1, B-RAF, B-RAFV600E, RET, and to a lesser extent FGFR2 and TIE2.

Phase I trials established a dosing regimen of 160 mg daily for 21 days of a 28 day cycle and demonstrated hand-foot syndrome, fatigue, diarrhea, and hypertension as the predominant side effects. Regorafenib demonstrated consistent bioavailability between subjects.  $T_{1/2}$  ranged from 20-40 hours, with relative stability of plasma concentrations between doses. It is metabolized into two pharmacologically active compounds, M2 and M5, which reach similar concentrations as the parent compound at steady state.

Regorafenib is an FDA-approved therapy for metastatic colorectal cancer that has progressed on prior therapy with 5-fluorouracil, oxaliplatin, irinotecan, anti-angiogenic therapy, and, if KRAS wild-type, anti-EGFR therapy. This approval was based on a proven survival benefit from the phase III CORRECT trial, which compared regorafenib to placebo in a 2:1 ratio in colorectal cancer that had progressed on all standard therapies. Participants randomized to regorafenib in that trial received 160 mg daily for three weeks out of a four-week cycle. Overall survival improved in the regorafenib arm to 6.4 months, compared to 5.0 months in the placebo arm (hazard ratio 0.77, 95% CI 0.64-0.94,  $p=0.0052$ ). Grade 3-4 toxicities in this trial with regorafenib included hand-foot syndrome (17%), fatigue (10%), diarrhea (7%), hypertension (7%), and rash (6%). Very few objective responses were seen with regorafenib (1% versus 0.4% with placebo), implying a cytostatic effect on the tumor.

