A second phase III trial conducted in Asia, the CONCUR study, identical in design to the CORRECT trial, confirmed the results. In this study, overall survival improved with regorafenib (8.8 months) compared to placebo (6.3 months) (HR 0.55, CI 0.40-0.77,  $p=0.00016$ ). The objective response rate was 4% in the regorafenib arm. Grade 3-4 adverse events were similar to those seen in the CORRECT trial, including hand-foot syndrome (16%), hypertension (11%), liver abnormalities (7% hyperbilirubinemia, 7% elevated ALT, 6% elevated AST), hypophosphatemia (7%), lipase elevation (6%), and rash (6%). Additionally, two grade 5 adverse events (cardiac arrest and death NOS) were possibly attributable to the drug.

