### ***2.8 Rationale for Clinical Trial***

In summary, previous studies have indicated that autophagy may be a mechanism of resistance to both antiangiogenic and cytotoxic drugs. Multiple phase I trials have shown that HCQ is well-tolerated with multiple forms of chemotherapy, and specifically with the combination of FOLFOX/bevacizumab in colorectal cancer, as well as with sorafenib. Based on very striking (Table 1) preclinical data that support the further addition of HDAC inhibition, this trial is proposed as a test of principle that augmented autophagy inhibition can render a purely antiangiogenic therapy more effective. Since regorafenib alone is associated with a 1% response rate, we would view a 15% response rate with the combination as promising and worth developing further.

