6.1.7 Table 8: Potential Toxicities of Regorafenib (from Stivarga Package Insert)

Adverse Reactions	STIVARGA (N=500)		Placebo (N=253)	
	Grade		Grade	
	All %	≥ 3 %	All %	≥ 3 %
General disorders and administration site conditions				
Asthenia/fatigue	64	15	46	9
Pain	29	3	21	2
Fever	28	2	15	0
Metabolism and nutrition disorders				
Decreased appetite and food intake	47	5	28	4
Skin and subcutaneous tissue disorders				
HFSR/PPES	45	17	7	0
Rash	26	6	4	<1
Gastrointestinal disorders				
Diarrhea	43	8	17	2
Mucositis	33	4	5	0
Investigations				
Weight loss	32	<1	10	0
Infections and infestations				
Infection	31	9	17	6
Vascular disorders				
Hypertension	30	8	8	<1
Hemorrhage*	21	2	8	<1
Respiratory, thoracic and mediastinal disorders				
Dysphonia	30	0	6	0
Nervous system disorders				
Headache	10	<1	7	0

\* Fatal outcomes observed.

Other clinically important adverse reactions observed more commonly in less than 10% of Stivarga-treated patients and at a higher incidence than in placebo-treated patients included the following: alopecia (7.6% vs. 1.6%), taste disorder (7.6% vs. 2.4%), musculoskeletal stiffness (6.0% vs. 2.0%), dry mouth (4.8% vs. 2.0%), hypothyroidism (4.2% vs. 0.4%), tremor (2.0% vs. 0.0), gastroesophageal reflux (1.4% vs. 0.0), and gastrointestinal fistula (0.8% vs. 0.4%).

Keratoacanthoma/squamous cell carcinoma of the skin occurred in 0.09% of 1100 Stivarga-treated patients across open-label or placebo-controlled clinical trials.

\*\*For complete information about regorafenib, please see the FDA package insert

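### Section 7.1.2 gives 1% as the phase III response rate for regorafenib and tests against it, but section 2.5 reports 1% in one phase III trial and 4% in another, and no reason is given for using only the lower rate

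*Combined protocol and SAP*

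**What the plan says.** Section 7.1.2 (Phase II) introduces the benchmark with "Single agent regorafenib showed ORR of 1% in phase III trials in advanced colorectal cancers", in the plural. It takes 1% as the null proportion and 15% as the "improved rate (alternative proportion) of 15"%. The test is an exact binomial test at a one-sided 0.05 level, with a stated power of 84% at 20 patients. The plan is to enrol 26 patients at the recommended phase II dose, and the calculation assumes at least 20 are evaluable. The number of responders needed to reject is not given.

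Section 2.8 repeats the benchmark, "Since regorafenib alone is associated with a 1% response rate", and adds "we would view a 15% response rate with the combination as promising and worth developing further".

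Section 2.5 reports two phase III trials of regorafenib. For the first: "Very few objective responses were seen with regorafenib (1% versus 0.4% with placebo"). The second, run in Asia, is described as "identical in design to the CORRECT trial, confirmed the results", and for it: "The objective response rate was 4% in the regorafenib arm".

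Section 7.2 plans 95% confidence intervals for progression-free survival, overall survival, duration of response and toxicity rates. It does not mention an interval for the response rate.

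**The concern.** The protocol's own background does not support the statement in 7.1.2. One of its two phase III trials gave 1%; the other gave four times that. Neither 7.1.2 nor 2.8 mentions the 4%, and no section says why it was set aside.

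The trial has no control arm, so any claim of improvement over regorafenib rests on this single figure. The cut-off is only two responders, and at that level the false-positive rate is sensitive to small changes in the assumed historical rate. A reader of the final report could take a two-responder result as an improvement on what phase III trials showed for regorafenib, when it would still be compatible with the rate in one of those trials.

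**Working it through.** **Inputs.** Null 1%, alternative 15%, one-sided level 0.05, n=20 evaluable at minimum and 26 planned (7.1.2). Reported regorafenib response rates 1% and 4% (2.5).

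**Formula.** For X responders among n at true rate p, P(X≥2) = 1 − (1−p)^n − n·p·(1−p)^(n−1).

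**Cut-off.** One responder is not enough: P(X≥1) at 1% is 1 − 0.99^20 = 0.182 at n=20 and 1 − 0.99^26 = 0.230 at n=26. Two are enough:
- n=20: 1 − 0.8179 − 0.1652 = 0.0169.
- n=26: 1 − 0.7700 − 0.2022 = 0.0277.

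P(X≥1) and P(X≥2) both rise with n, so the cut-off is 2 for every n from 20 to 26.

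**The plan's power figure.** At 15% with n=20: 1 − 0.0388 − 0.1368 = 0.8244, so 82.4% against the stated 84%, a difference of 1.6 points. At n=26: 1 − 0.0146 − 0.0671 = 0.9183, so 91.8%.

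**Error of the same rule if the combination adds nothing to regorafenib.** The rates between 1% and 4% are assumed, to show the range.

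| Regorafenib-alone rate | n=20 | n=26 |
|---|---|---|
| 1% | 1.7% | 2.8% |
| 1.5% | 3.6% | 5.8% |
| 2% | 6.0% | 9.5% |
| 3% | 12.0% | 18.3% |
| 4% | 19.0% | 27.9% |

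The 4% row in full:
- n=20: 1 − 0.4420 − 0.3683 = 0.1897.
- n=26: 1 − 0.3460 − 0.3748 = 0.2792.

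**Where the error reaches 5%.** Solving P(X≥2) = 0.05 for p gives 1.81% at n=20 and 1.38% at n=26.

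**What two responders exclude.** The exact (Clopper-Pearson) one-sided 95% lower bound for two responders solves the same equation. It is therefore 1.8% for 2/20 (10% observed) and 1.4% for 2/26 (7.7% observed). Both exceed 1%; neither exceeds 4%.

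**The case against.** **1% is a reasonable benchmark.** The first trial is the one on which approval rested. The second was run in Asia, while this study is at one US centre. The populations may also differ in prognosis: by section 2.5, placebo survival was 6.3 months in the second trial against 5.0 in the first, and regorafenib survival was 8.8 against 6.4. An identical design does not mean an identical population. All of this stands, and it is why the null need not change. But the protocol does not offer any of it as the reason, and it does not make 1% the rate in both trials.

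**4% is a single point estimate.** This also stands. A reader might infer that the trial's true false-positive rate is 19% to 28%, or that the null ought to be 4%. The documents support neither. The 4% is the higher of two reported estimates, has its own sampling error, and comes from a trial whose size is not given.

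**Pooling would settle it.** A reader might want to combine the two trials. Table 8 shows "STIVARGA (N=500") from a package insert without naming the trial, and the second trial's arm size appears nowhere. A pooled rate would rest on an invented denominator.

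**The 15% in section 2.8 already guards against over-claiming.** Read as an observed rate, it would need 3/20 or 4/26, where the lower bounds are 4.2% and 5.4%. But 2.8 does not say whether 15% is an observed or a true rate, 7.1.2 uses it only as the alternative, and neither ties it to how a positive test is reported.

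**Conclusion.** The attribution in 7.1.2 is wrong by the protocol's own account, and the choice of the lower rate is unexplained. The test is valid as a test against 1%, with error of 1.7% to 2.8%. It has little margin: the nominal 5% is passed at a regorafenib-alone rate of about 1.8% (n=20) or 1.4% (n=26). The 19.0% and 27.9% figures apply only if that rate is truly 4%, and should be read as the extreme case. The minimum positive result shows a rate above 1% and nothing about 4%.

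These results assume the exact binomial test as stated and 20 to 26 evaluable patients. They need no assumption about the size of either phase III trial.

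A reader might go further and require the lower bound to exceed 4% before any improvement is claimed. That would amount to a second test against a noisy figure. At a true 15%, its chance of success moves between 42.5% and 63.0% depending on how many of 20 to 26 patients are evaluable. The documents do not call for such a rule.

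The power discrepancy is small. It does not undermine the sample size, since exact power at n=20 is still above 80%.

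**What to change.** In 7.1.2 and 2.8:
- Give both phase III rates, 1% and 4%. Describe the test as one against the lower estimate and state the reason for that choice.
- Keep the 1% test and the sample size. State the cut-off of 2 or more responders for 20 to 26 evaluable patients, with its error at 1% (1.7% to 2.8%) and at 4% (19.0% to 27.9%).
- Plan to report the response rate with its exact one-sided 95% lower bound. Word a positive test as exceeding 1%, with the 4% shown beside it.
- Restate the exact power at n=20 as 82.4% (91.8% at n=26).

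The cost is wording only: no more patients and no change to the formal test. The downside is a more modest statement when only two responders are seen. At a true rate of 15%, exactly two would occur in 22.9% of trials at n=20 (0.8244 − 0.5951, where 0.5951 is the chance of three or more) and in 14.8% at n=26 (0.9183 − 0.7704). The stated power at n=20 is also 1.6 points lower.

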#### ***4.5 DLT Definition and Escalation Decision Process***

Dose Limiting Toxicities will be defined by toxicity occurring during the first 4 weeks of this study. Any non-hematologic AE of Grade 3 or higher that is judged to be probably treatment-related will be considered a DLT with the exceptions of fatigue; rash attributable to regorafenib; or nausea, vomiting, or diarrhea that has improved to Grade < 1 within 72 hours. Any non-hematologic AE of Grade 4 or higher of any duration that is judged to be probably treatment-related will be considered a DLT except for elevations of lipase and/or amylase in the absence of clinical pancreatitis.

The following hematologic DLT will be considered if any occurs in the first cycle:

- 1) grade 4 neutropenia lasting more than 7 days
- 2) febrile neutropenia (T > 100.4 F in presence of ANC <500)
- 3) platelet count less than 25,000/mm^3
- 4) platelet count less than 50,000/mm^3 with clinically significant hemorrhage

If a DLT is observed in exactly 1 patient in the first cohort of 3, the cohort will be expanded to 6. If a DLT occurs in 2 or more patients per cohort, then the cohort one dose below will be the declared the MTD provided that at least 6 patients have been treated at that level with fewer than one third having DLTs. The rules for dose escalation and cohort size are outlined in Table 3. No intra-patient dose escalation is planned.

***Evaluable Patients:*** Patients will be evaluable for toxicity if they have taken one dose of HCQ and entinostat. Patients who experience a dose-limiting toxicity will be evaluable for the cohort after at least one dose of HCQ and one dose of entinostat. To be considered for evaluability in a Phase I cohort in the absence of dose-limiting toxicity, patients should have completed  $\geq 85\%$  of HCQ doses, and at least 3 of 4 entinostat doses. Phase II patients will be evaluable for response if they have completed 85% of their expected dose of HCQ and at least 3 doses of entinostat in the initial 4 weeks, in the absence of progression. Patients who do not meet these criteria will be replaced. In the unexpected event of excess toxicity at dose level 1, there is provision (Table 3) for a dose reduction of both HCQ and entinostat.

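### Section 7.1.2 states 84% power for an exact test with 20 patients; that test has 82.4% power, a small error that leaves the rule and enrolment unchanged

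*Combined protocol and SAP*

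**What the plan says.** The Phase II primary endpoint is response rate, tested in a single arm. Section 7.1.2 gives the design in three steps.

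- Enrolment: "We will enroll a total 26 patients at the RP2D, including those treated during the phase I portion of the study".
- Basis of the calculation: "Sample size calculations are based on an assumption of at least 20 evaluable patients".
- Power: "With 20 patients, an exact binomial test with a 0.05 one-sided significance level will have 84% power to detect an improvement", with a null response rate of 1% and an alternative of 15%.

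The section does not print the number of responses that rejects the null, the attained type I error, or the power for any number other than 20. Section 4.5 adds, for Phase II patients who fall short on drug exposure in the first four weeks: "Patients who do not meet these criteria will be replaced".

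**The concern.** The power sentence names an exact test and supplies every input: sample size, level, sidedness, null and alternative. An exact binomial power has one value for those inputs, so 84% is either right or wrong, and a reader can check it in a few lines. It is also the only operating characteristic that the plan gives for the Phase II primary test. If it were badly wrong, the trial could be underpowered for the 15% response rate that section 2.8 treats as worth pursuing. If it is slightly wrong, the cost is an incorrect figure in the plan, liable to be copied into later reports.

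**Working it through.** **Inputs, all from section 7.1.2:** exact binomial test, one-sided level 0.05, p0 = 0.01, p1 = 0.15, n = 20, stated power 84%.

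**Step 1: cut-off at n = 20.** Find the smallest r with P(X ≥ r | p0) ≤ 0.05.

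- r = 1: 1 − 0.99^20 = 0.182, which is too large.
- r = 2: 1 − 0.99^20 − 20(0.01)(0.99^19) = 1 − 0.8179 − 0.1652 = 0.0169, which is allowed.

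The test rejects at 2 or more responses, and its attained type I error is 1.7%.

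**Step 2: power at n = 20.**

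P(X ≥ 2 | 0.15) = 1 − 0.85^20 − 20(0.15)(0.85^19) = 1 − 0.0388 − 0.1368 = 0.8244.

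Exact power is 82.4%, against 84% stated. The difference is 84 − 82.4 = 1.6 points.

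**Step 3: can the stated 84% be reproduced?** Not by the named test. Two approximations at n = 20, one-sided 0.05, come near it:

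- Normal approximation with continuity correction: Φ[(0.15 − 0.01 − 1/40 − 1.645·√(0.01·0.99/20)) / √(0.15·0.85/20)] = 0.837, which rounds to 84%.
- Arcsine approximation: Φ[2(arcsin√0.15 − arcsin√0.01)·√20 − 1.645] = 0.845.

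The normal approximation without correction gives 0.902. The documents do not say how the figure was obtained.

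**Step 4: the same exact calculation for larger n.** One response is never enough (at n = 26, P(X ≥ 1 | 0.01) = 0.230), so the cut-off stays at 2.

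| Evaluable patients | Reject at | Type I error at 1% | Power at 15% |
|---|---|---|---|
| 20 | ≥ 2 | 1.7% | 82.4% |
| 21 | ≥ 2 | 1.9% | 84.5% |
| 22 | ≥ 2 | 2.0% | 86.3% |
| 23 | ≥ 2 | 2.2% | 88.0% |
| 24 | ≥ 2 | 2.4% | 89.4% |
| 25 | ≥ 2 | 2.6% | 90.7% |
| 26 | ≥ 2 | 2.8% | 91.8% |

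The exact test first reaches 84% at 21 patients.

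**The case against.** The strongest defence is that the gap is trivial. It is under 2 points, power remains above 80%, and one evaluable patient beyond the minimum already gives 84.5%. All of that stands, and it is why the point is minor. It does not make the figure correct: a tolerance suits approximate formulas, whereas this sentence names an exact test whose power rounds to 82%.

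Three stronger readings are tempting, and the documents do not support them.

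- *That the plan sets up a 26-patient test and misreports its power.* Section 7.1.2 gives 26 as enrolment and 20 as the least number evaluable, and the power sentence is tied to 20. Quoting power at the minimum is ordinary conservative practice.
- *That replacement will bring the analysis close to 26.* The Phase II replacement rule in section 4.5 concerns drug exposure in the first four weeks. Section 10.1 also requires disease re-evaluation, and section 4.7 puts the first scan at 8 weeks, so a patient can avoid replacement and still lack a scan. Replacement in the cohort that establishes the recommended dose (section 4.3) excludes those who leave because of toxicity, and section 7.3 makes the 20 additional patients an upper limit. The evaluable number could lie anywhere from 20 to 26.
- *That 84% came from a particular approximation, such as the arcsine.* Arcsine gives 84.5% (0.8453, which rounds to 85%), and the continuity-corrected normal gives 83.7%. The source cannot be determined.

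Nor is the rejection rule truly hidden. It follows uniquely from the stated test, and an exact test keeps type I error at or below 0.05. Printing the cut-off is a convenience to the reader, not the repair of an ambiguity.

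**Conclusion.** The point holds as a minor error of arithmetic. For the test, level, rates and sample size that section 7.1.2 names, exact power is 82.4% and not 84%; the statement is 1.6 points too high. The result rests only on the section's own inputs and on the usual exact rule, which rejects at the smallest count with null tail probability no more than 0.05.

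Nothing else moves. The cut-off is 2 responses throughout the range 20 to 26, type I error at the 1% null lies between 1.7% and 2.8%, and power lies between 82.4% and 91.8%. The sample size remains adequate against an 80% standard. The values for 26 are the upper end of that range and apply only if every enrolled patient is evaluable; they do not describe a test that the plan has specified.

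**What to change.** Replace the power sentence in section 7.1.2 with wording such as:

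> The null is rejected if at least 2 responses are seen among evaluable patients. With the minimum of 20 evaluable patients the exact one-sided type I error is 0.017 and power at 15% is 82%; if all 26 enrolled at the RP2D are evaluable these are 0.028 and 92%.

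The cost is one sentence and a slightly less favourable figure for the 20-patient case. Enrolment, the test and its level stay as they are.
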